### **3.5. Safety Endpoints**

Per the protocol, the active safety monitoring duration is defined as up to 36 days after the last dose of GO or start of subsequent anticancer therapy (which includes consolidation and/or conditioning regimens), whichever occurs first. Also, per protocol any event of VOD/SOS will be reported as SAE during the entire study duration. Any occurrences of VOD/SOS will be recorded in the CRF for entire study duration of 12 months regardless of causality, subsequent anticancer therapy or HSCT. Further details of the AE collection are described in the protocol Section 8.

The on-treatment period for reporting is defined as the time from the first dose of study treatment through end of study follow-up.

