8.1.4.1. Reporting SAEs to Pfizer Safety

All SAEs occurring in a patient during the active collection period are reported to Pfizer Safety on the CT SAE Report Form.

SAEs occurring in a patient after the active collection period has ended are reported to Pfizer Safety if the investigator becomes aware of them; at a minimum, all SAEs that the investigator believes have at least a reasonable possibility of being related to investigational product must be reported to Pfizer Safety. Follow up by the investigator continues throughout and after the active collection period and until the event or its sequelae resolve or stabilize at a level acceptable to the investigator, and Pfizer concurs with that assessment.

If a patient starts a subsequent anticancer therapy (eg, consolidation, and/or conditioning regimen, or HSCT), SAEs occurring during the above-indicated active collection period (ie, within 36 days of last dose of GO) must still be reported to Pfizer Safety irrespective of any intervening treatment and causality.

Incidence of VOD/SOS will be reported for the entire study duration of 12 months, regardless of causality, or start of subsequent anticancer therapy (eg, consolidation and/or conditioning regimen, or HSCT). All cases of VOD/SOS must be reported as SAEs (recorded on the CRF and CT SAE Report Form).

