8.1.4.2. Recording Non-serious AEs and SAEs on the CRF

During the active collection period, both non-serious AEs and SAEs are recorded on the CRF.

Follow-up by the investigator may be required until the event or its sequelae resolve or stabilize at a level acceptable to the investigator, and Pfizer concurs with that assessment.

If a patient begins a new anticancer therapy, the recording period for non-serious AEs ends at the time the new treatment is started; however, SAEs must continue to be recorded on the CRF during the above-indicated active collection period.

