9.3.2. Analysis of Secondary Endpoints

9.3.2.1. Safety Analysis

9.3.2.1.1. Adverse Events

AEs will be graded by the investigator according to the CTCAE version 4.03 and coded using the Medical Dictionary for Regulatory Activities (MedDRA). The focus of AE summaries will be on Treatment Emergent Adverse Events, those with initial onset or increasing in severity after the first dose of study medication. The number and percentage of patients who experienced any AE, SAE, treatment related AE, and treatment related SAE will be summarized according to worst toxicity grades. CCI

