#### **3.5.1. Adverse Events**

AEs will be graded by the investigator according to the CTCAE version 4.03 and coded using the Medical Dictionary for Regulatory Activities (MedDRA).

An adverse event is considered treatment emergent relative to a given treatment if the event starts after the first dose of study treatment. Although time will be collected on the exposure

CRF, time will not be collected on the AE CRF. Refer to Section 5.3.1, for details, but adverse events occurring on the same day as the first dose of study treatment will be considered to have occurred during the on-treatment period.

Because the protocol requires collection of VOD/SOS for the entire duration of the study, all collected AEs that start after the first dose of study treatment will be included as treatment emergent.

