### **5.2.4. Definition of Cycle and Cycle Day**

For Cycle 1 and Cycle 2 the actual start date for each patient will be determined from the first start date of dosing from the respective CRF exposure page with a dose recorded.

If Cycle 2 is administered, then the actual stop date for Cycle 1 will be calculated as the start date of Cycle 2 minus one day.

For the last Cycle, actual stop date will be calculated as the minimum of the last dose + 36 and the start date of subsequent anticancer therapy.

The cycle day will be calculated as Cycle day = Date of the assessment/event – cycle start date + 1.

The cycle day will be displayed in all relevant data listings.

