#### 6.6.3.2. Hy's Law Assessment

**Liver function tests:** Alanine aminotransferase (ALT), aspartate aminotransferase (AST), Alkaline Phosphatase (ALP), and total bilirubin (TBILI) are used to assess possible drug induced liver toxicity.

An evaluation of drug-induced serious hepatotoxicity (eDISH) by scatterplots of using all data from the on treatment period will be produced to assess hepatotoxicity and to identify any potential Hy's Law cases. This summary does NOT indicate actual Hy's law cases.

- Maximum serum ALT vs maximum total bilirubin including reference lines at ALT=3×ULN and total bilirubin=2×ULN.
- Maximum serum AST) vs maximum total bilirubin including reference lines at AST=3×ULN and total bilirubin=2×ULN.

In addition, a listing of all total bilirubin, ALT, AST and alkaline phosphatase values for patients with a post-baseline total bilirubin  $\geq 2\times$ ULN, ALT  $\geq 3\times$ ULN or AST  $\geq 3\times$ ULN will be provided.

Summary of liver function tests will include the following categories. The number and percentage of patients with each of the following during the on-treatment period will be summarized:

- ALT  $\geq 3\times$ ULN, ALT  $\geq 5\times$ ULN, ALT  $\geq 10\times$ ULN, ALT  $\geq 20\times$ ULN
- AST  $\geq 3\times$ ULN, AST  $\geq 5\times$ ULN, AST  $\geq 10\times$ ULN, AST  $\geq 20\times$ ULN
- (ALT or AST)  $\geq 3\times$ ULN, (ALT or AST)  $\geq 5\times$ ULN, (ALT or AST)  $\geq 10\times$ ULN, (ALT or AST)  $\geq 20\times$ ULN
- TBILI  $\geq 2\times$ ULN
- Concurrent ALT  $\geq 3\times$ ULN and TBILI  $\geq 2\times$ ULN
- Concurrent AST  $\geq 3\times$ ULN and TBILI  $\geq 2\times$ ULN
- Concurrent (ALT or AST)  $\geq 3\times$ ULN and TBILI  $\geq 2\times$ ULN
- Concurrent (ALT or AST)  $\geq 3\times$ ULN and TBILI  $\geq 2\times$ ULN and ALP  $> 2\times$ ULN
- Concurrent (ALT or AST)  $\geq 3\times$ ULN and TBILI  $\geq 2\times$ ULN and ALP  $\leq 2\times$ ULN or missing

Concurrent measurements are those occurring on the same date.

Categories will be cumulative, i.e., a participant with an elevation of AST  $\geq 10\times$ ULN will also appear in the categories  $\geq 5\times$ ULN and  $\geq 3\times$ ULN. Liver function elevation and possible Hy's Law cases will be summarized using frequency counts and percentages.

Summary of liver function tests will also be provided by Cycle (1, 2, Follow-up).

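### The SAP's on-treatment and treatment-emergent windows run to the end of follow-up for all AEs and liver values, and several safety outputs do not separate the GO period from later therapy

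*SAP*

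**What the plan says.** SAP 3.5 first restates the protocol's monitoring window: the "active safety monitoring duration is defined as up to 36 days after the last dose of GO or start of subsequent anticancer therapy", whichever comes first. The next paragraph sets a different and much longer window for reporting: "The on-treatment period for reporting is defined as the time from the first dose of study treatment through end of study follow-up". SAP 3.5.1 then says that "all collected AEs that start after the first dose of study treatment will be included as treatment emergent", and gives the study-long collection of VOD/SOS as the reason.

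The AE tables in SAP 6.6.1 use treatment-emergent events by default. In SAP 6.6.3.2 the eDISH plots "using all data from the on treatment period will be produced", and the liver-test table uses the same period. SAP 6.6.3 takes the worst on-treatment grade for the laboratory shift tables.

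Elsewhere the SAP already has a shorter cut-off. For the last cycle, SAP 5.2.4 says the "actual stop date will be calculated as the minimum of the last dose + 36 and the start date of subsequent anticancer therapy". SAP 5.2.5 labels AEs that start after that date as Follow-up. The SAP's version history justifies this cycle definition by consistency with the safety reporting period and with standard definitions that consider later anticancer therapy.

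On collection, Protocol 8.1.4.2 says that "the recording period for non-serious AEs ends at the time the new treatment is started". Under Protocol 8.1.4.1, SAEs within 36 days of the last dose "must still be reported to Pfizer Safety irrespective of any intervening treatment and causality". Protocol Table 1, footnote 17, limits follow-up chemistry to patients in whom VOD/SOS occurs.

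**The concern.** The reason given in SAP 3.5.1 supports a 12-month window for VOD/SOS, which has its own analysis in SAP 6.6.1.1. It does not call for the same window for every other event and every liver value.

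The study has to describe the safety of single-agent fractionated GO, including haemorrhage and hepatic risk. Patients with relapsed or refractory AML may go on to further chemotherapy, conditioning or HSCT, each with its own infections, bleeding and liver toxicity. Where a table does not separate the periods, its rate depends partly on how soon patients switch therapy and on which data are still collected afterwards. A reader of an AESI or SAE table could not tell which events arose before the switch.

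**Working it through.** The plan states no figure on this point, so there is none to reproduce. The check compares the windows, the collection rules and the table specifications.

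**1. Length of the windows.** Inputs: doses on Days 1, 4 and 7 (Protocol 5.4.2); cut-off at last dose + 36 or new therapy if earlier (SAP 5.2.4); Cycle 2 no later than 42 days after Cycle 1 Day 7 (Protocol 6.2.1); 12 months on study, taken as 365 days. Dosing is assumed to be on schedule.
- One cycle: 7 + 36 = Day 43. Remaining: 365 − 43 = 322 days; 322/365 = 88%.
- Two cycles, latest start: 7 + 42 = Day 49; last dose 49 + 6 = Day 55; 55 + 36 = Day 91. Remaining: 365 − 91 = 274 days; 274/365 = 75%.

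So 75% to 88% of the nominal on-treatment window lies after active monitoring, and more if new therapy starts early. This measures the window, not the amount of data in it.

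**2. What is collected after a switch.**
- Non-serious AEs: recording stops (Protocol 8.1.4.2).
- SAEs: CRF recording continues to last dose + 36 days. After that they go to Pfizer Safety if the site learns of them (Protocol 8.1.4.1); later CRF recording is required only for VOD/SOS (Protocol 6.2.5).
- Blood counts: stop at new therapy (Table 1, footnote 12).
- Follow-up chemistry: only with VOD/SOS (footnote 17). Footnote 19 adds institutional tests after HSCT for suspected or diagnosed VOD/SOS.

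Other anticancer therapy is held until remission status is determined (Protocol 5.7), typically Day 21 to 28 (Protocol 6.2.2.4). In a one-cycle patient, CRF recording of non-VOD SAEs after a switch therefore spans about 43 − 28 = 15 to 43 − 21 = 22 days.

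**3. Which outputs separate the periods.**

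| Output | Split in the SAP |
|---|---|
| All-causality TEAEs by SOC, PT and maximum grade (6.6.1) | Cycle 1, Cycle 2, Follow-up |
| Liver-test categories (6.6.3.2) | Cycle 1, Cycle 2, Follow-up |
| VOD/SOS (6.6.1.1) | Before and after follow-up HSCT |
| High-level summary, including the Grade 5 row (6.6.1) | None specified |
| SAE and treatment-related tables (6.6.1) | None specified |
| AESI tables, including hepatotoxicity with all VOD/SOS (6.6.1) | None specified |
| Basic results (6.6.1.2) | None specified |
| Laboratory shift tables (6.6.3) | None specified |
| eDISH plots (6.6.3.2) | None specified |

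Text is redacted directly after the by-cycle sentence in SAP 6.6.1, so this table reflects the visible text only.

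**4. An illustration.** Last dose Day 7, new therapy Day 25, first serious infection Day 33. Day 33 is before Day 43, so the event is recorded. It counts in the infection AESI and SAE tables with nothing to mark it. In the by-cycle TEAE table it falls under Follow-up, because the last cycle ended on Day 25.

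**5. Size per patient.** A patient whose only event in a row arises after the switch adds 1/50 = 2.0 percentage points among adults, or 1/56 = 1.8 with all patients combined.

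**The case against.** A reader might infer that the SAP lengthened a shorter protocol definition of treatment emergence. It did not. Protocol 9.3.2.1.1 defines treatment-emergent events as "those with initial onset or increasing in severity after the first dose of study medication", also with no end date. Counting every collected event is the inclusive choice, and the SAP gives its reason openly.

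A reader might also infer that a year of events and liver values under later therapy flows into the GO tables. The collection rules do not support that. Non-serious AEs and routine blood counts stop at the switch, follow-up chemistry is tied to VOD/SOS, and CRF recording of other SAEs is required only to last dose + 36 days. SAP 6.6.1 takes seriousness and grade from the AE CRF; only the fatal-event table in 6.6.1.2 is stated to use the safety database.

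The existing splits help too. The main AE and liver-test tables show Follow-up separately, VOD/SOS is divided by HSCT, and SAP 6.6.2 tabulates deaths within 36 days of the last dose. Treatment-related tables are screened by investigator causality, although a missing relationship counts as related.

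Finally, cutting the headline tables at the switch would move delayed GO-related SAEs out of them. That is a real cost.

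All of this stands, and it narrows the point. It does not supply a split in the remaining outputs, and it makes late liver data more selective: they come from patients with VOD/SOS, while other transplanted patients contribute few or none.

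**Conclusion.** The point holds as a gap in presentation. One window to the end of follow-up applies to all AEs and liver values on a rationale that covers VOD/SOS alone. The high-level, SAE, treatment-related, Grade 5, AESI, laboratory-shift, basic-results and eDISH outputs can mix GO-period findings with later ones, and late liver maxima are selectively sampled. The clearest inflow is SAEs between a switch and last dose + 36 days, plus VOD/SOS and the chemistry it triggers.

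The total effect cannot be derived, because the documents give neither a switching rate nor a post-switch event rate. A reader might size it by assuming both, but any such range would only restate the assumptions. The supportable figure is 2 percentage points per affected adult, assuming 50 adults in the safety set. The 15-to-22-day span assumes one cycle, dosing on schedule and remission assessment at the typical time.

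**What to change.** Apply the cut-off of SAP 5.2.4 and 5.2.5, min(last GO dose + 36 days, start of subsequent anticancer therapy), as a flag in the outputs listed above with no split. In each table show events and values up to the cut-off, those in Follow-up, and the all-period total. A patient may appear in both periods but counts once in the total. In the eDISH plots, mark values taken after the cut-off. SAP 5.2.5 words its Follow-up rule for AEs only, so state that it also covers laboratory values. Keep the 12-month window for VOD/SOS in SAP 6.6.1.1.

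Showing both periods beside the total keeps delayed GO-related SAEs in view, which truncation would not. The cost is extra columns and one date flag; the dates are already collected.

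Separately, reconcile the protocol's recording rules. Table 1, footnote 16, and Section 6.2.4 end AE recording at 36 days or new therapy, whichever is first, while Sections 8.1.4.1 and 8.1.4.2 continue SAEs past the start of new therapy. The content of the Follow-up columns depends on which rule sites follow.

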#### **3.5.1. Adverse Events**

AEs will be graded by the investigator according to the CTCAE version 4.03 and coded using the Medical Dictionary for Regulatory Activities (MedDRA).

An adverse event is considered treatment emergent relative to a given treatment if the event starts after the first dose of study treatment. Although time will be collected on the exposure

CRF, time will not be collected on the AE CRF. Refer to Section 5.3.1, for details, but adverse events occurring on the same day as the first dose of study treatment will be considered to have occurred during the on-treatment period.

Because the protocol requires collection of VOD/SOS for the entire duration of the study, all collected AEs that start after the first dose of study treatment will be included as treatment emergent.

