8.1.4. Time Period for Collecting AE/SAE Information

The time period for actively eliciting and collecting AEs and SAEs (“active collection period”) for each patient begins from the time the patient provides informed consent, which is obtained before the patient’s participation in the study (ie, before undergoing any study-related procedure and/or receiving investigational product) through and including a minimum of 36 calendar days after the last administration of the investigational product.

For patients who are screen failures, the active collection period ends when screen failure status is determined.

Any patient with VOD/SOS will be monitored for the study duration of 12 months from enrollment as described in [Section 7.4.1](#).

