8.3. Severity Assessment

If required on the AE page of the CRF, the investigator will use the adjectives MILD, MODERATE, or SEVERE to describe the maximum intensity of the AE. For purposes of consistency, these intensity grades are defined as follows:	
MILD	Does not interfere with subject's usual function.
MODERATE	Interferes to some extent with subject's usual function.
SEVERE	Interferes significantly with subject's usual function.

Note the distinction between the severity and the seriousness of an AE. A severe event is not necessarily an SAE. For example, a headache may be severe (interferes significantly with the subject's usual function) but would not be classified as serious unless it met one of the criteria for SAEs, listed above.

Investigators should report AEs using concise medical terminology (verbatim) as well as collect on the CRF the appropriate Common Terminology Criteria for Adverse Events (CTCAE) (Version 4.03, Publish Date: 14 June 2010, NCI CTCAE) listed in the Cancer Therapy Evaluation Program. New protocols of projects that have been utilizing a previous version may continue to use that version.

If required on the AE page of the CRF, the investigator will use the following definitions of severity in accordance with the current CTCAE version to describe the maximum intensity of the adverse event.

Grade	Clinical Description of Severity
0	No change from normal or reference range (This grade is not included in the Version 4.03 CTCAE document but may be used in certain circumstances.)
1	MILD adverse event
2	MODERATE adverse event
3	SEVERE adverse event
4	LIFE-THREATENING consequences; urgent intervention indicated
5	DEATH RELATED TO adverse event

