### 6.6.1. Adverse Events

The following general considerations will be applied to AE summaries:

All analyses will be based on treatment emergent events unless otherwise specified. Treatment emergent is defined in Section 3.5.1. AEs not considered treatment emergent will be flagged in data listings (as applicable to listings needed to be compliant with ICH required listings).

- For summaries including CTCAE grade, patients will be counted according to the worst grade for the particular PT or SOC and will also include a total across grades.
- For summaries including toxicity grade, as described in Section 5.3.2, in the case that a patient has events with missing and non-missing toxicity grades, the maximum of the non-missing grade will be displayed. Missing grade will only be displayed in the event that only one event has been reported for a patient and the grade is missing.
- There will also be a row for the number and percentage of patients reporting at least 1 AE.
- For summaries including SOC, the number and percentage of patients with at least 1 AE in that SOC will be reported.
- The denominator for percentages will be the number of patients treated in the group being summarized.
- Each patient will be counted only once within each SOC and PT.
- In summaries of treatment related AEs, if the relationship to study treatment is missing on the CRF, it will be assumed to be related to treatment.

A high level summary of adverse events (all causality and also for treatment related events) will include the number and percentage of patients with:

- Any Adverse Event
- Serious AE

- Adverse Events with CTCAE Grade 3-4
- Grade 5 events
- AEs that caused the subject to be discontinued from the study
- AEs with Action Taken with Study Treatment was Drug Withdrawn but AE did not Cause the Subject to be discontinued from the study
- AEs leading to dose reductions or temporary discontinuations (note that no dose reductions are specified per protocol and the CRF used the term interruptions rather than temporary discontinuations)
- Additionally, the number of events will be provided. Each unique adverse event at the PT level for a patient is included in the count.

Seriousness, toxicity grade, action taken will be as reported by the investigator on the adverse event CRF.

**Summaries by SOC and PT** in decreasing frequency within SOC based on frequencies observed for adult patients will be provided for:

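### The SAP defines treatment-emergent adverse events by start date only and drops, without saying so, the protocol's criterion of worsening after first dose

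*SAP*

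**What the plan says.** Protocol section 9.3.2.1.1 puts the focus of the adverse event (AE) summaries on treatment-emergent events and defines them as "those with initial onset or increasing in severity after the first dose of study medication". That gives two routes into the tables: new onset, or worsening.

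SAP section 3.5.1 keeps only the first: "An adverse event is considered treatment emergent relative to a given treatment if the event starts after the first dose of study treatment". The section closes on the same rule, saying that "all collected AEs that start after the first dose of study treatment will be included as treatment emergent". The reason given there is the collection of VOD/SOS over the whole study. That explains why late events are kept; it says nothing about worsening. Because the AE form records no time of day, the section adds a Day 1 convention: "adverse events occurring on the same day as the first dose of study treatment will be considered to have occurred during the on-treatment period".

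SAP section 6.6.1 makes the definition the default for AE reporting: "All analyses will be based on treatment emergent events unless otherwise specified". Of the remaining events it says that "AEs not considered treatment emergent will be flagged in data listings", as far as such listings are required.

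On data collection, protocol section 8.1.4 states that the active collection period "begins from the time the patient provides informed consent", and protocol section 6.1 allows screening up to 28 days before dosing. Protocol section 8.3 asks the investigator "to describe the maximum intensity of the AE", where the AE page requires it.

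**The concern.** The two documents give different answers for the same event. Suppose bleeding starts during screening at a low grade, becomes severe after GO and is kept as one record. Under the protocol it is treatment emergent. Under the SAP it is not, even if the investigator judges the worsening serious and related to GO.

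Safety is a secondary objective, and the protocol summary names haemorrhage among the risks that the FDA post-marketing requirements asked the sponsor to assess. Haemorrhage and myelosuppression are AEs of special interest in SAP section 3.5.1.1. Leaving out worsened events can only lower the reported counts. It also sits oddly with the SAP's cautious choices elsewhere: section 6.6.1 treats missing causality as related, and section 5.3.1.1 resolves missing start dates towards treatment emergence.

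**Working it through.** The plan states no figure to reproduce. The check is a comparison of texts, followed by applying each rule to the possible kinds of record.

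**Step 1: does another part of the SAP restore the worsening criterion?** No.
- Section 5.2.5 assigns AEs to cycles by start date.
- Section 5.3.1.1 imputes missing dates and does not use grade.
- Section 6.6.1 refers back to section 3.5.1 for the definition.
- Table 1 lists several changes to the AE summaries but not this one. It records changes between SAP versions rather than departures from the protocol, so its silence alone proves little. No other SAP section declares or explains the difference either.

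**Step 2: apply both definitions.**

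| Record | Protocol 9.3.2.1.1 | SAP 3.5.1 and 5.3.1.1 |
|---|---|---|
| Onset after Day 1 | Counted | Counted |
| Onset on Day 1, time unknown | Depends on time of onset or on worsening | Counted |
| Start date missing, event ended after first dose | Not addressed | Counted; start set to first-dose date |
| Onset before Day 1, worsening entered as a new record dated after first dose | Counted | Counted |
| Onset before Day 1, grade rises after GO, one record | Counted | **Not counted** |
| Onset before Day 1, no worsening | Not counted | Not counted |

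The documents conflict to the patient's loss in one row only: a known start date before Day 1, a rise in grade after GO, and a single record.

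**Step 3: can that row occur?** Yes. AEs are collected from consent, and up to 28 days may pass before dosing. Neither document says that a rise in grade opens a new record. Recording the maximum intensity of an AE points towards one record per event but does not settle it.

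**Step 4: which outputs lose the event?** Under the default in SAP section 6.6.1: the high-level summary, the tables by SOC and PT, by maximum grade, serious, treatment related, and leading to drug withdrawal or interruption, and the AE tables of special interest.

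**Step 5: where does worsening still appear?**
- Laboratory grades: shift tables from baseline to worst grade (SAP 6.6.3).
- Liver tests: on-treatment threshold table (SAP 6.6.3.2).
- QTc: shift from baseline to worst value (SAP 6.6.5.4).
- Fatal AEs: a table drawn from the safety database and not labelled treatment emergent (SAP 6.6.1.2), so its scope is unclear.

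None of these shows a non-fatal clinical event such as bleeding.

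**Step 6: size.** The documents give no rate of pre-dose AEs and no rate of worsening, so the number of patients cannot be computed. Only the unit can: the denominator is the number treated, and if all 50 planned adults are treated, one omitted patient lowers a given row by 1/50 = 2 percentage points. Rows such as any AE may not move at all, because the same patient may have another counted event.

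**The case against.** The strongest reply is that few records meet all the conditions. Conditions already present at screening go to medical history (protocol 6.1, SAP 6.5.1.3). If one of these later worsens and is entered as an AE, its start date falls after first dose and the SAP counts it. The exposed events are then mainly those arising between consent and Day 1. Cytopenia, liver-test and QTc worsening is tabulated elsewhere. The SAP is also allowed to differ: protocol section 9 and SAP section 2 call for an amendment only for major changes to the primary endpoint or its analysis. And if each record holds only a maximum grade, adding a sentence to the SAP would not help, because no pre-dose grade exists for comparison.

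Most of this stands, and it limits the point. A reader might infer that worsened pre-dose events vanish from every AE table; Step 2 and the fatal AE table show otherwise. A reader might also infer that patients enter with cytopenia, infection and bleeding that will all be lost. The documents do not say that such conditions become pre-dose AE records, and uncontrolled or active infection is an exclusion criterion (protocol 4.2).

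Two things do not stand. Permission to modify the protocol does not excuse an undeclared change. And the recording rule that would make the SAP wording harmless is in neither document.

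**Conclusion.** The SAP is wrong as written against the protocol's own definition, within a narrow scope. It omits the worsening criterion without declaration or rationale. A single-record AE that starts between consent and the day before first dose and rises in grade after GO is left out of the treatment-emergent summaries. The omission itself can act only downward on reported AE frequency, and it falls mainly on clinical, non-laboratory events that begin in screening.

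The mismatch of texts is certain. The loss of patients from the tables is conditional: it assumes that at least some grade increases are kept on the original record, which depends on CRF instructions that the documents do not give. A reader might want to attach a patient count; the documents support none. The primary QTcF analysis and the sample size are unaffected. The point should be corrected because it touches a secondary objective and the remedy is cheap.

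**What to change.** 1. **SAP 3.5.1.** Define an AE as treatment emergent if its start date is on or after the first-dose date, or if it began earlier and after first dose reaches a CTCAE grade above the highest pre-dose grade for that same event.
2. **Recording rule.** State in the SAP and in the CRF completion guidance that a rise in grade after first dose is entered as a new AE record with its own start date. Without this, item 1 cannot be programmed where a record holds only the maximum grade.
3. **Existing records.** SAP version 2 is dated 21 April 2021 and refers to enrolment during the pandemic, so data recorded without such a rule may already exist. For each single record with onset before Day 1 that was ongoing at first dose, query the pre-dose grade. If it cannot be obtained, count the event as treatment emergent.

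The cost is a short SAP amendment, a line of CRF guidance and a small number of data queries. The downside is slightly higher reported AE rates, part of which may come from events counted by default when the pre-dose grade is unknown; a footnote giving their number would deal with that. Declaring the departure from protocol section 9.3.2.1.1 with a rationale would make it transparent, but would not put the events back in the tables.
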